1.2. Endpoints

Primary Endpoints

Phase 1b:

- Recommended Phase 2 Dose (RP2D) of ibrutinib in combination with MEDI4736
- Safety and tolerability of ibrutinib in combination with MEDI4736

Phase 2:

- Overall Response Rate (ORR)

Secondary Endpoints

Phase 1b:

- Overall response rate (ORR)
- Duration of response (DOR)

Phase 2:

- DOR
- Progression-free survival (PFS)
- Overall survival (OS)

Safety Assessments

Safety and tolerability assessments include adverse events, clinical laboratory tests, and vital signs.

1.3. Statistical Hypotheses

There is no hypothesis testing for Phase 1b. The primary objective of Phase 2 is to evaluate overall response rate (ORR) for the combination therapy at RP2D. Hypothesis testing will be conducted to address this objective as follows:

Null hypothesis (H_0): $P \leq x\%$; where P denotes overall response rate.

Alternative hypothesis (H_a): $P > y\%$; where P denotes overall response rate.

For FL cohort, a true response rate of 30% (H_0) versus 50% (H_a) will be tested. For DLBCL cohort, a true response rate of 15% (H_0) versus 35% (H_a) will be tested.

1.4. Sample Size Determination**Phase 1b:**

6-36 subjects for DLT assessment (6-9 subjects in up to 4 dose de-escalation cohorts, regardless of tumor type).

Phase 2:

Approximately 73 response-evaluable subjects (including those subjects treated at the RP2D in Phase 1b but with tumor type as defined for Phase 2).

For FL:

A maximum of 39 response-evaluable subjects (including those subjects treated at the RP2D in Phase 1b and with tumor type of FL) will be enrolled. An interim analysis will be performed after 19 subjects are evaluable for tumor response after completing at least 1 response assessment. If only 6 or fewer responders ($\leq 6/19$) are observed, the Sponsor may consider discontinuation of this cohort.

The null hypothesis that the true ORR is 30% will be tested against a one-sided alternative that the ORR is 50%. The null hypothesis will be rejected if 17 or more responses are observed in the 39 subjects. This design yields a 1-sided type I error rate of 0.05 and power of 80% when the true ORR is 50%. This statistical design including number of subjects and number of responders follows the statistical framework of Simon's minimax two-stage design (Simon, 1989). Enrollment will continue while the interim analysis is performed.

For DLBCL:

A maximum of 34 response-evaluable subjects with GCB and non-GCB (inclusive of subjects treated at the RP2D in Phase 1b in the unselected DLBCL population) will be enrolled at a 1:1 ratio approximately.

An interim analysis will be performed after 9 subjects are evaluable for tumor response after completing at least 1 response assessment. If only 1 or fewer responder ($\leq 1/9$) is observed, the Sponsor may consider discontinuation of this cohort.

The null hypothesis that the true ORR is 15% will be tested against a one-sided alternative that the ORR is 35%. The null hypothesis will be rejected if 9 or more responses are observed in the 34 subjects. This design yields a 1-sided type I error rate of 0.05 and power of 80% when the true ORR is 35%. This statistical design including number of subjects and number of responders follows the statistical framework of Simon's optimal two-stage design (Simon 1989). Enrollment will continue while the interim analysis is performed.

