An interim analysis will be performed after 9 subjects are evaluable for tumor response after completing at least 2 response assessments. If only 1 or fewer responder ($\leq 1/9$) is observed, the Sponsor may consider discontinuation of this cohort (see Section 12.11).

The null hypothesis that the true ORR is 15% will be tested against a one-sided alternative that the ORR is 35%. The null hypothesis will be rejected if 9 or more responses are observed in the 34 subjects. This design yields a 1-sided type I error rate of 0.05 and power of 80% when the true ORR is 35%. The statistical design including number of subjects and number of responders follows the statistical framework of Simon's optimal two-stage design (Simon, 1989). Enrollment will continue while the interim analysis is performed.

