After the RP2D of ibrutinib in combination with MEDI4736 is defined, enrollment in Phase 2 will commence.

Phase 2:

Two tumor types will be enrolled in separate cohorts as part of this protocol:

- Follicular lymphoma (FL) (grade 1, 2, or 3A)
- Diffuse large B cell lymphoma (DLBCL)

For FL: n = 39

The FL cohort will enroll 39 response-evaluable subjects. An interim analysis will be performed after 19 subjects are evaluable for tumor response after completing at least 1 response assessment. If only 6 or fewer responders ($\leq 6/19$) are observed, the Sponsor may consider discontinuation of this cohort; however, assessment of biomarkers (that may aid in prospective enrichment of responders) or tumor measurements (showing clinically relevant tumor reductions, ie, 40%, that fit the criteria for SD) may support continued enrollment.

For DLBCL: n = 34

Subjects with germinal center B-cell (GCB) and non-GCB subtypes will be enrolled at a 1:1 ratio approximately. The DLBCL cohort will enroll 34 response-evaluable subjects. An interim analysis will be performed after 9 subjects are evaluable for tumor response after completing at least 1 response assessment. If only 1 or fewer responder ($\leq 1/9$) is observed, the Sponsor may consider discontinuation of this cohort; however, assessment of biomarkers (that may aid in prospective enrichment of responders) or tumor measurements (showing clinically relevant tumor reductions, ie, 40%, that fit the criteria for SD) may support continued enrollment.

In the DLBCL cohort, additional prospectively identified non-GCB subjects may be enrolled if a 22% ORR (2/9) is not achieved at the interim analysis in the unselected DLBCL population so that at least a total of 16 subjects with the non-GCB subtype are evaluated.

Note: The Phase 2 subjects include all of those response-evaluable subjects treated at R2PD in Phase 1b but with tumor type as defined for Phase 2.

During the Phase 2 portion of the study, if a subject discontinues study drug prior to the first tumor response assessment for reasons other than progressive disease, the subject may be replaced.

The primary analysis will occur at least 12 months after the last FL subject is enrolled and at least 9 months after the last DLBCL subject is enrolled.

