1.5.2. Phase 2 Analyses

An interim analysis is planned for each tumor type:

An interim analysis for FL will be performed after 19 subjects are evaluable for tumor response after completing at least 1 response assessment. If only 6 or fewer responders ($\leq 6/19$) are observed, the Sponsor may consider discontinuation of this cohort; however, assessment of biomarkers (that may aid in prospective enrichment of responders) or tumor measurements (showing clinically relevant tumor reductions, ie, 40%, that fit the criteria for SD) may support continued enrollment.

An interim analysis for DLBCL will be performed after 9 subjects are evaluable for tumor response after completing at least 1 response assessment. If only 1 or fewer responder ($\leq 1/9$) is observed, the Sponsor may consider discontinuation of this cohort; however, assessment of biomarkers (that may aid in prospective enrichment of responders) or tumor measurements (showing clinically relevant tumor reductions, ie, 40%, that fit the criteria for SD) may support continued enrollment.

The primary efficacy analysis will occur at least 12 months after the last FL subject is enrolled and at least 9 months after the last DLBCL subject is enrolled.

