1.6. Testing Procedure and Level of Significance

The 2-sided significance level for the final analysis of primary endpoint (ORR) will be 0.05. Analyses of secondary endpoints will be performed using the same significance level.

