4. EFFICACY AND SAFETY ANALYSES

4.1. Efficacy Analyses

Efficacy endpoints and analysis methods are summarized in Table 1.

Table 1: Summary of Efficacy Analyses

Endpoint	Definition	Analysis Method
Primary Endpoint		
Overall Response Rate (ORR)	Proportion of subjects achieving the best overall responses of complete response (CR) or partial response (PR) with confirmation per the investigator using the Revised Criteria for Response Assessment of Malignant Lymphoma (Cheson 2014)	
Primary (Response-evaluable population)
 
 Proportion and 2-sided 95% CI based on exact Binomial distribution (Clopper-Pearson) 
Sensitivity (Treated population)
 
 Proportion and 2-sided 95% CI based on exact Binomial distribution (Clopper-Pearson) Waterfall plot of best change from baseline of tumor load from target lesion(s) 
Subgroup (Response-evaluable and treated population): For the DLBCL cohort, a subgroup analysis will also be conducted to calculate ORR and its 95% CI for
 
 GCB and non-GCB DLBCL types per IHC test GCB, ABC and Unclassified DLBCL types per GEP test
Secondary Endpoints		
Duration of Response (DOR)	Duration of time from the date of initial response to the date of disease progression or the date of death due to any cause, whichever occurs first	
Primary (Response-evaluable population)
 
 Kaplan-Meier estimate
Progression Free Survival (PFS)	Duration of time from the first dose date of study treatment (ibrutinib or MEDI4736) to the first documentation of disease progression or death	
Primary (Treated population)
 
 All PD and death considered as events regardless of any anticancer therapy prior to PD Kaplan-Meier curve

Endpoint	Definition	Analysis Method
	from any cause, whichever occurs first.	
Overall Survival (OS)	Duration of time from the first dose date of study treatment (ibrutinib or MEDI4736) to the date of death due to any cause	Primary (Treated population) 
 All death considered as events regardless any anticancer therapy prior to death Kaplan-Meier curve

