5. MODIFICATION OF ANALYSIS TO THE PROTOCOL

Below is the major change made to the analyses in the protocol:

- The timing of interim analysis for the FL cohort is changed from “An interim analysis will be performed after 19 subjects are evaluable for tumor response after completing at least 2 response assessments” to “An interim analysis will be performed after 19 subjects are evaluable for tumor response after completing at least 1 response assessment” due to the number of early treatment discontinuations prior to 2 response assessments.
- The timing of the interim analysis for the DLBCL cohort is changed from “An interim analysis will be performed after 9 subjects are evaluable for tumor response after completing at least 2 response assessments.” to “An interim analysis will be performed after 9 subjects are evaluable for tumor response after completing at least 1 response assessment.
- Because of the substantial number of subjects who discontinued treatment due to PD after one post-baseline tumor assessment, the sponsors (Pharmacyclics and AstraZeneca) decided to hold the enrolment during the interim analysis.
- The terminology ‘Safety Assessments’ instead of ‘Safety Endpoints’ is used in Section 1.2 safety analysis part.

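### DLBCL: the stated one-sided type I error of 0.05 is guaranteed only if the 1/9 stop is followed; the plan makes the stop optional, so at N = 34 the error can reach 5.9%

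*SAP*

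**What the plan says.** SAP 1.4 and Protocol 10.4.2 test a true DLBCL response rate of 15% against 35%. An interim look follows 9 evaluable subjects, the cohort has at most 34, and "The null hypothesis will be rejected if 9 or more responses are observed in the 34 subjects". Both documents attribute the design to Simon's optimal two-stage framework. SAP 1.4 then claims: "This design yields a 1-sided type I error rate of 0.05 and power of 80% when the true ORR is 35" percent.

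The stop at 1/9 or fewer is discretionary. SAP 1.5.2 says "the Sponsor may consider discontinuation of this cohort; however, assessment of biomarkers (that may aid in prospective enrichment of responders) or tumor measurements" showing shrinkage that still counts as stable disease may justify going on. SAP 1.1 adds that "additional prospectively identified non-GCB subjects may be enrolled if a 22% ORR (2/9) is not achieved at the interim analysis", so that at least 16 non-GCB subjects are evaluated. It does not say whether they fall within the 34.

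Two other places bear on this but do not settle it:
- SAP 4.1, Table 1 makes the primary analysis an exact proportion with a two-sided 95% confidence interval, with no interim condition.
- SAP 5 moves the interim from two response assessments to one. It reports a "substantial number of subjects who discontinued treatment due to PD after one post-baseline tumor assessment" and says the sponsors "decided to hold the enrolment during the interim analysis". It does not make the stop mandatory.

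**The concern.** In a Simon design, a trial that fails stage 1 cannot reject the null. The quoted error and power depend on that. Here the plan allows the cohort to go on after 1/9 or fewer, and its final rule counts responses in 34 subjects however the interim went. Each path that fails the interim and still ends with 9 or more responses adds to the type I error.

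The numerical excess is small. What matters more in practice is that the plan does not say whether 9/34 reached after a failed interim is a valid rejection of the null. At a true response rate of 15%, a failed interim is more likely than not (59.9%, if every eventual responder among the first 9 is already counted), so this should be settled before the data are seen.

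**Working it through.** **Inputs** (SAP 1.3 and 1.4; Protocol 10.4.2): null rate 0.15, alternative 0.35, stage 1 of 9 subjects with the stop at 1 or fewer, 25 further subjects to reach 34, rejection at 9 or more. Let X1 be the responses in the first 9 and X2 those in the next 25. All figures are exact binomial.

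**1. Reproduce the plan's figure (stop followed).** Type I error = sum over x = 2 to 9 of P(X1 = x | 9, 0.15) × P(X2 ≥ 9 − x | 25, 0.15).

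| x | P(X1 = x) | P(X2 ≥ 9 − x) | product |
|---|---|---|---|
| 2 | 0.2597 | 0.0695 | 0.01805 |
| 3 | 0.1069 | 0.1615 | 0.01727 |
| 4 | 0.0283 | 0.3179 | 0.00900 |
| 5 | 0.0050 | 0.5289 | 0.00264 |
| 6 to 9 | | | 0.00048 |
| **Sum** | | | **0.04744** |

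The same sum at 0.35 gives power 0.8107. An exhaustive search for Simon's optimal design at these rates (error at most 0.05, power at least 0.80) returns the plan's design exactly. The stated 0.05 and 80% are therefore that design's nominal limits.

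**2. Add the failed-interim paths at 0.15.**
- 0/9: 0.2316 × 0.00797 = 0.00185
- 1/9: 0.3679 × 0.02547 = 0.00937
- Total: 0.01122

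**3. Stop never followed.** 0.04744 + 0.01122 = 0.0587, which equals P(X ≥ 9 | 34, 0.15). Power is P(X ≥ 9 | 34, 0.35) = 0.8914.

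**4. Stop sometimes followed.** The documents give no override probability. If a failed interim is continued with probability q, equal at 0/9 and 1/9 and independent of later outcomes, the error is 0.04744 + 0.01122q.
- q = 0.5: 0.0531
- Error equal to 0.05: q = (0.05 − 0.04744) / 0.01122 = 0.228
- Always stopped at 0/9, always continued at 1/9: 0.04744 + 0.00937 = 0.0568

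**5. More than 34 subjects.** If added non-GCB subjects took the total past 34 with the cutoff still 9 and the stop ignored, the error would be 6.9% at an assumed N of 35 and 8.0% at 36.

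**6. FL for contrast.** The FL rule (at most 6/19, then at least 17/39, null 30%) gives 4.55% with the stop followed and 4.998% with it ignored. It stays within 0.05 either way.

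**7. Power if rejection required at least 2/9.** SAP 5 places the interim after one assessment, while Table 1 counts best response with confirmation. Let f be the share of eventual responders among the first 9 who are already counted at the interim. The documents give no value, so f is assumed. Each term in step 1 is multiplied by P(at least 2 of x visible | x, f).

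| f | type I error | power at 35% |
|---|---|---|
| 1.00 | 4.74% | 81.1% |
| 0.95 | 4.56% | 79.1% |
| 0.90 | 4.35% | 76.9% |
| 0.80 | 3.89% | 71.4% |

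The chance of a failed interim also depends on f. At f = 1 it is 59.9% under the null and 12.1% under the alternative; at f = 0.90 these become 65.2% and 17.1%.

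**The case against.** The strongest reply is that nothing is miscalculated. The text names Simon's framework, and the stated figures are right for that design. That stands: the gap is an unstated condition. The citation alone does not supply the condition, though, because the same plan sets out grounds for continuing after a failed interim and never says that 9/34 then ceases to count. The enrolment hold in SAP 5 does not supply it either.

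A second reply is that the effect is small. Under the null, failing the interim and still reaching 9/34 has a probability of 1.1% even if the stop is always ignored. That also stands, and it limits the weight of the point. The early progressions reported in SAP 5 do not show that the DLBCL interim failed or was likely to fail, since that statement names no cohort.

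A third reply is that SAP 1.6 says "The 2-sided significance level for the final analysis of primary endpoint (ORR) will be 0.05". At that level the cutoff would have to be at least 10/34, where the error is 2.1% with the stop followed and 2.4% with it ignored, so this excess would not arise. That is correct. The point here depends on the one-sided 0.05 of SAP 1.4 governing, and the two-sided statement is a separate conflict to reconcile.

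**Conclusion.** The point holds in a limited form. At N = 34 and cutoff 9, the one-sided type I error lies between 4.74% (stop followed) and 5.87% (never followed), so the stated 0.05 is not guaranteed. The excess is at most 0.9 points and comes with higher power (89.1% against 81.1%).

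A reader might infer three stronger things that the documents do not support:
- **That 0.05 fails unless the stop is binding.** The error stays within 0.05 while no more than about 23% of failed interims are continued, under the assumptions in step 4.
- **That 5.9% is an absolute ceiling.** It is the ceiling only for 34 subjects. The stated maximum argues against a larger number, but the plan does not say whether added non-GCB subjects count within it.
- **That a binding rule would cost nothing.** The 81.1% power holds only if every eventual responder among the first 9 is already counted at the interim. With one assessment required, that is not assured; an assumed 95% already takes power below 80%.

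**What to change.** In SAP 1.4 and Protocol 10.4.2, replace the DLBCL type I error statement with: *one-sided type I error 4.7% if the ≤1/9 stop is followed, up to 5.9% if it is not (N = 34, cutoff 9)*. Add a sentence saying that any added non-GCB subjects are either counted within the 34 or analysed descriptively outside the ≥9/34 test. Without that sentence the 5.9% is not assured.

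This costs about two sentences in each document. The sample size, the cutoff and the Sponsor's freedom to continue do not change. The price is openly accepting an error that may slightly exceed 0.05.

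If the Sponsor prefers to keep 0.05 by allowing rejection only after at least 2/9, it must also define what counts as a response at the one-assessment interim, given that the final endpoint requires confirmation, and restate power using a justified share of responders visible by then. Compared with a stop that is never followed, this option gives up at least 89.1 − 81.1 = 8.0 points of power as rounded, and more if responses come late.

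Reconcile SAP 1.6 with SAP 1.4 separately. Keeping the 9/34 cutoff means SAP 1.6 should state a one-sided 0.05.

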1.5. Planned Analyses

1.5.1. Phase 1b Analyses

A Dose Level Review Committee will be established to evaluate the safety data from each cohort of the Phase 1b on an ongoing basis. Dose de-escalation will follow the 6+3 design described in Section 3.1.1 and up to 4 cohorts including 3 dose de-escalation cohorts (1, -1A, -1B, and -2) will be enrolled if needed to determine the RP2D for the combination therapy.

1.5.2. Phase 2 Analyses

An interim analysis is planned for each tumor type:

An interim analysis for FL will be performed after 19 subjects are evaluable for tumor response after completing at least 1 response assessment. If only 6 or fewer responders ($\leq 6/19$) are observed, the Sponsor may consider discontinuation of this cohort; however, assessment of biomarkers (that may aid in prospective enrichment of responders) or tumor measurements (showing clinically relevant tumor reductions, ie, 40%, that fit the criteria for SD) may support continued enrollment.

An interim analysis for DLBCL will be performed after 9 subjects are evaluable for tumor response after completing at least 1 response assessment. If only 1 or fewer responder ($\leq 1/9$) is observed, the Sponsor may consider discontinuation of this cohort; however, assessment of biomarkers (that may aid in prospective enrichment of responders) or tumor measurements (showing clinically relevant tumor reductions, ie, 40%, that fit the criteria for SD) may support continued enrollment.

The primary efficacy analysis will occur at least 12 months after the last FL subject is enrolled and at least 9 months after the last DLBCL subject is enrolled.

1.6. Testing Procedure and Level of Significance

The 2-sided significance level for the final analysis of primary endpoint (ORR) will be 0.05. Analyses of secondary endpoints will be performed using the same significance level.

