10.4.1 Phase 1b

Dose de-escalation will follow the 6+3 design described in Section 3.1 and up to 4 cohorts including 3 dose de-escalation cohorts (1, -1A, -1B, and -2) will be enrolled if needed to determine the RP2D for the combination therapy.

A total of 6-36 subjects eligible for DLT assessment will be enrolled into Phase 1b of the study with 6-9 DLT-evaluable subjects (regardless of tumor type) per dose cohort. Subjects are considered DLT-evaluable if they receive the assigned dose of study treatment (both ibrutnib and MEDI4736) and complete the safety follow-up through the DLT-observation period.

Cohorts -1A and -1B are two parallel dose de-escalation cohorts. Subjects will be enrolled concurrently in the sequence of -1A followed by -1B. For example, the first available subject goes to -1A, the second to -1B, the third to -1A, the fourth to -1B, etc. However, when one dose de-escalation cohort needs an additional 3 subjects to evaluate DLTs, all available subjects will be assigned to this cohort first.

Subjects in Phase 1b who were dosed at the RP2D may also be included in the Phase 2 analysis.

10.4.2 Phase 2

Approximately 73 response-evaluable subjects (including those subjects treated at the RP2D in Phase 1b but with tumor type as defined for Phase 2) will be enrolled.

For FL:

A maximum of 39 response-evaluable subjects (including those subjects treated at the RP2D in Phase 1b but with tumor type of FL) will be enrolled. An interim analysis will be performed after 19 subjects are evaluable for tumor response after completing at least 2 response assessments. If only 6 or fewer responders ($\leq 6/19$) are observed, the Sponsor may consider discontinuation of this cohort (see Section 12.11).

The null hypothesis that the true ORR is 30% will be tested against a one-sided alternative that the ORR is 50%. The null hypothesis will be rejected if 17 or more responses are observed in 39 subjects. This design yields a 1-sided type I error rate of 0.05 and power of 80% when the true ORR is 50%. This statistical design including number of subjects and number of responders follows the statistical framework of Simon's minimax two-stage design (Simon, 1989). Enrollment will continue while the interim analysis is performed.

For DLBCL:

A maximum of 34 subjects with GCB and non-GCB subtypes (including those subjects treated at the RP2D in Phase 1b but with tumor type of GCB and non-GCB DLBCL) will be enrolled at a 1:1 ratio approximately.

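### SAP 1.6 sets the final ORR test at two-sided 0.05, but the rejection counts in SAP 1.4 and Protocol 10.4.2 are a one-sided 0.05 rule; the two disagree at 17/39 (FL) and 9/34 (DLBCL)

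*SAP*

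**What the plan says.** SAP 1.6 (Testing Procedure and Level of Significance) reads: "The 2-sided significance level for the final analysis of primary endpoint (ORR) will be 0.05". It continues: "Analyses of secondary endpoints will be performed using the same significance level".

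SAP 1.4 describes the same test differently. Each cohort has a one-sided alternative, and for FL: "This design yields a 1-sided type I error rate of 0.05 and power of 80% when the true ORR is 50"%. The DLBCL text is the same with 35% as the alternative. The decision rules are explicit and appear in the protocol synopsis, Protocol 10.4.2 and SAP 1.4. Protocol 10.4.2 says for FL: "The null hypothesis will be rejected if 17 or more responses are observed in 39 subjects", and for DLBCL: "The null hypothesis will be rejected if 9 or more responses are observed in the 34 subjects".

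SAP 4.1, Table 1, plans the ORR estimate with a two-sided 95% Clopper-Pearson interval as the primary analysis, and Kaplan-Meier methods only for DOR, PFS and OS. SAP section 5 lists the changes from the protocol; none concerns the level, the sidedness or the counts. SAP 1.3 writes the null as P at or below x% and the alternative as P above y%, where y is the design value (50% or 35%).

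**The concern.** ORR is the only endpoint with a stated hypothesis test, and the SAP gives that test two levels without saying which decides. If the conclusion could never depend on the choice, this would be untidy and no more. It can depend on it: a result exactly at the written threshold in either cohort is a rejection under SAP 1.4 and not a rejection at two-sided 0.05. In an open-label single-arm study that leaves a boundary result to be interpreted after the data are known. The report could also say that the null was rejected beside a primary-analysis interval that contains the null rate. Nor can two-sided 0.05 and the stated 80% power both hold at the planned sample sizes with the stop applied.

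**Working it through.** **Inputs (SAP 1.4; Protocol 10.4.2).** FL: null 30%, alternative 50%, stop at 6 or fewer of 19, reject at 17 or more of 39. DLBCL: null 15%, alternative 35%, stop at 1 or fewer of 9, reject at 9 or more of 34.

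**Formula.** With the stop applied, P(reject) = Σ over x₁ > r₁ of Bin(x₁; n₁, p) × P(Bin(n − n₁, p) ≥ r − x₁). With the stop ignored, P(reject) = P(Bin(n, p) ≥ r).

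**Step 1: reproduce the plan's figures.** With the stop applied, the counts give type I error 0.0455 and power 80.4% (FL), and 0.0474 and 81.1% (DLBCL). Enumerating two-stage designs at one-sided 0.05 and 80% power returns these same designs as the minimax (FL) and the optimal (DLBCL). The counts therefore belong to a one-sided 0.05 test, as SAP 1.4 says.

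**Step 2: apply two-sided 0.05 at and just above the thresholds.**

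| Count | One-sided p, single stage | Doubled p | Minimum-likelihood p | Doubled two-stage p | 95% Clopper-Pearson |
|---|---|---|---|---|---|
| FL 17/39 | 0.04998 | 0.100 | 0.079 | 0.091 | 27.8% to 60.4% |
| FL 18/39 | 0.0242 | 0.048 | 0.035 | 0.046 | 30.1% to 62.8% |
| DLBCL 9/34 | 0.0587 | 0.117 | 0.087 | 0.095 | 12.9% to 44.4% |
| DLBCL 10/34 | 0.0240 | 0.048 | 0.028 | 0.041 | 15.1% to 47.5% |

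Every version fails at 17/39 and 9/34 and passes one count higher. Mid-p (0.074 and 0.083) and score (0.064 and 0.061) versions also fail at the two disputed counts. At 16/39 and 8/34 neither rule rejects. The thresholds that match two-sided 0.05 are therefore 18/39 and 10/34; they are derived here and are not in the documents.

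**Step 3: how often it matters (stop applied).** The probability of landing on the disputed count is P(reject at r) − P(reject at r + 1).

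- At the alternatives: FL 0.8036 − 0.7224 = 0.0812; DLBCL 0.8107 − 0.7433 = 0.0674. At least one cohort: 1 − (1 − 0.0812)(1 − 0.0674) = 0.143.
- At the nulls: FL 0.04550 − 0.02295 = 0.02255; DLBCL 0.04744 − 0.02055 = 0.02689. At least one cohort: 1 − (1 − 0.02255)(1 − 0.02689) = 0.049.

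**Step 4: power if two-sided 0.05 governed.**

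| Rule | Type I error, stop applied | Power, stop applied | Type I error, stop ignored | Power, stop ignored |
|---|---|---|---|---|
| FL ≥17/39 (written) | 0.0455 | 80.4% | 0.04998 | 83.2% |
| FL ≥18/39 | 0.0230 | 72.2% | 0.0242 | 73.9% |
| DLBCL ≥9/34 (written) | 0.0474 | 81.1% | 0.0587 | 89.1% |
| DLBCL ≥10/34 | 0.0206 | 74.3% | 0.0240 | 80.4% |

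The third row carries a side result. The stop is optional in SAP 1.5.2 ("the Sponsor may consider discontinuation of this cohort; however, assessment of biomarkers" and tumor measurements may support continuing). If it is always overridden, the written DLBCL count has one-sided type I error 0.0587, above the stated 0.05. The FL count stays just under 0.05 either way.

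**The case against.** The best defence is that SAP 1.6 is loose wording with no effect. The counts are stated three times, always with a one-sided alternative and a one-sided error rate, while SAP 1.6 names no test, statistic or count. The only planned ORR output is an estimate with a two-sided 95% interval, which is what a two-sided 0.05 level matches. The second sentence of SAP 1.6 extends the level to endpoints that have only Kaplan-Meier analyses, which again suggests interval coverage. Much of this stands: the counts most likely govern, and the power loss in step 4 is conditional on a reading that is probably not intended. It does not clear the text, because a section on testing gives a significance level for the primary endpoint that does not match the rule, and the interval itself contains the null rate at both boundary counts.

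A literal two-sided test also has a lower tail: doubled p is at or below 0.05 at 0 to 5 of 39 and at 0 of 34. The directional null in SAP 1.3 means such results cannot count as rejections in favor of the treatment, so the disagreement is properly limited to counts above the null rate.

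It is also fair to say that the optional stop and the notation in SAP 1.3 are separate matters. They are secondary here. The stop bears on the wording only because it decides whether the 9/34 rule delivers the level that a corrected SAP 1.6 would claim.

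**Conclusion.** The concern holds. The SAP gives its one tested endpoint two conflicting levels, and the conclusion differs at 17/39 and at 9/34. With the stop applied, the chance of landing on a disputed count at the design alternatives is 8.1% in FL, 6.7% in DLBCL and 14.3% in at least one cohort; at the nulls it is 2.3%, 2.7% and 4.9%. Under the written counts, power is as stated (80.4% and 81.1%). Only if two-sided 0.05 were applied literally would it fall to 72.2% and 74.3%. SAP 1.6 is probably the sentence in error, so this should be fixed, but it does not undermine the design.

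The figures assume exactly 39 and 34 evaluable subjects, independent cohorts and a constant response rate. They do not describe the route in SAP 1.1 by which "additional prospectively identified non-GCB subjects may be enrolled if a 22% ORR (2/9) is not achieved at the interim analysis".

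**What to change.** Rewrite SAP 1.6 to say that ORR is tested in each cohort at one-sided 0.05 by the rejection counts in SAP 1.4, and that the two-sided 95% interval is descriptive and is not the test. Replace its second sentence with the confidence-interval coverage for the secondary endpoints, since Table 1 plans no test for them.

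Add a note that the 9/34 rule has type I error 0.0474 only if the interim stop at 1 or fewer of 9 is followed, and 0.0587 if it is always overridden and 34 unselected subjects are still enrolled; neither figure covers the added non-GCB enrollment. In SAP 1.3, write the alternatives as P > 30% (FL) and P > 15% (DLBCL), with power evaluated at 50% and 35%. As written, rates between the null and the design value fall under neither hypothesis.

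This costs a few sentences of SAP text, with no extra subjects, no new analysis and no change to the rejection rule. If two-sided 0.05 is really intended, the rule does change: the counts become 18/39 and 10/34, SAP section 5 must list the change, and power must be restated as 72.2% and 74.3% with the stop applied.
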